6 STUDY PERIODS, TREATMENT REGIMENS AND POPULATIONS FOR ANALYSES

6.1 Study Periods

- Baseline period:
 - Baseline evaluations or events will be defined as evaluations or events that occur before the date and time of the first dose of study treatment. Evaluations (laboratory tests, pulse oximetry and vital signs) on the same date and time of the first dose of study treatment will be considered as baseline evaluations. Events (AEs) on the same date and time of the first dose of study treatment will not be considered as pre-treatment events.
 - In cases where the time (onset time of event or evaluation time and dosing time) is missing or not collected, the following definitions will apply:
 - ◆ Pre-treatment AEs will be defined as AEs with an onset date prior to but not including the day of the first dose of study treatment;
 - ◆ Baseline evaluations (laboratory tests, pulse oximetry and vital signs) will be defined as evaluations with a date on or prior to the day of first dose of study treatment.
 - If there are multiple valid assessments on or prior to the first dose of study treatment:
 - ◆ For laboratory tests, the latest non missing labs value on or before first dose date (and time if collected) will be used as the baseline in the analyses. For 'LIPASE' and 'GLUCOSE', for treated subjects only, the last predose assessment with non-missing toxicity grade will be considered as baseline. If multiple assessments exist with the same collection date (and time if collected) and entry date and time, then the first observation is used as baseline.

- Post baseline period:
 - On-treatment AEs will be defined as AEs with an onset date and time on or after the date and time of the first dose of study treatment (or with an onset date on or after the day of first dose of study treatment if time is not collected or is missing). For subjects who are off study treatment, AEs will be included if event occurred within a safety window of 30 days (or 100 days depending on the analysis) after the last dose of study treatment. No “subtracting rule” will be applied when an AE occurs both pre-treatment and post-treatment with the same preferred term and grade.
 - On-treatment evaluations (laboratory tests, pulse oximetry and vital signs) will be defined as evaluations taken after the day (and time, if collected and not missing) of first dose of study treatment. For subjects who are off study treatment, evaluations should be within a safety window of 30 days (or 100 days depending on the analysis) after the last dose of study treatment.
- Late-emergent drug-related AEs will be defined as drug-related AEs with an onset date greater than 100 days after the last dose of study treatment in subjects who are off study treatment.

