Laboratory Tests (includes blood and urine samples)	FU1 -yes FU2 - if toxicities are present		See Section 9.4.1 for additional details on tests required. 
 • CBC w/differential, PT/INR, and PTT • Chemistry panel (includes AST, ALT, total bilirubin, ALP, LDH, creatinine, BUN, glucose, albumin, Na, K, Cl, Ca, P, Mg, amylase, lipase) • Thyroid panel (includes TSH with reflexive free T3 and free T4) • Urine protein and urine creatinine (for UPCR, preferred) or urine dipstick for protein
Pregnancy Test	X		Serum or Urine. WOCBP only.
Efficacy Assessments			
Tumor Assessments	First tumor assessment post-baseline should be performed Week 12 (± 7 days) following randomization. Use same imaging method as was used at baseline.		Participants who discontinue study treatment without radiographic progression, confirmed by BICR, will continue tumor assessments according to the protocol specified schedule, even if new anti-tumor therapy has been initiated in the Follow-Up phase, until radiographic

- ^a Participants must be followed for at least 100 days after last dose of study treatment. Follow-up visit #1 (FU1) should occur 30 days from the last dose (+/- 7) days or can be performed on the date of discontinuation if that date is greater than 42 days from last dose. Follow-up visit #2 (FU2) occurs approximately 100 days (+/- 7 days) from last dose of study drug. Both Follow Up visits should be conducted in person.
- ^b Survival Follow-up visits to occur every 3 months from Follow-up Visit #2. Survival visits may be conducted in person or by telephone. BMS may request that survival data be collected on all treated participants outside of the 3 month specified window. At the time of this request, each participant will be contacted to determine their survival status unless the participant has withdrawn consent for all contact.

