7.6.2 Serious Adverse Events

Serious adverse events will be summarized by treatment group:

- Overall summary of SAEs by worst CTC grade (any grade, grade 3-4, grade 5) presented by SOC/PT.
- Overall summary of drug-related SAEs by worst CTC grade (any grade, grade 3-4, grade 5) presented by SOC/PT.

All analyses will be conducted using the 30-day safety window.

A by-subject SAE listing will be provided for the “enrolled subjects” population.

Note that for all intermediate/poor risk treated subjects in Arm A and Arm C, serious adverse events will be summarized by treatment group.

Similar tables will be presented for those subjects treated in Arm B.

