7.6.10.4 Additional Analyses

In addition, further analyses on specific laboratory parameters will be performed by treatment group:

Abnormal Hepatic Function Test

The number of subjects with the following laboratory abnormalities from on-treatment evaluations will be summarized by treatment group:

- ALT or AST > 3 x ULN, > 5 x ULN, > 10 x ULN and > 20 x ULN
- Total bilirubin > 2 x ULN

- ALP > 1.5 x ULN
- Concurrent (within 1 day) ALT or AST > 3 x ULN and total bilirubin > 1.5 x ULN
- Concurrent (within 30 days) ALT or AST > 3 x ULN and total bilirubin > 1.5 x ULN
- Concurrent (within 1 day) ALT or AST > 3 x ULN and total bilirubin > 2 x ULN
- Concurrent (within 30 days) ALT or AST > 3 x ULN and total bilirubin > 2 x ULN

The analyses will be conducted using the 30-day safety window.

A by-subject listing of these specific abnormalities will be provided.

Abnormal Thyroid Function Test

The number of subjects with the following laboratory abnormalities from on-treatment evaluations will be summarized by treatment group:

- TSH value > ULN and
 - with baseline TSH value \leq ULN
 - with at least one FT3/FT4 test value < LLN within 2-week window after the abnormal TSH test
 - with all FT3/FT4 test values \geq LLN within 2-week window after the abnormal TSH test
 - with FT3/FT4 missing within 2-week window after the abnormal TSH test.
- TSH < LLN and
 - with baseline TSH value \geq LLN
 - with at least one FT3/FT4 test value > ULN within 2-week window after the abnormal TSH test
 - with all FT3/FT4 test values \leq ULN within 2-week window after the abnormal TSH test
 - with FT3/FT4 missing within 2-week window after the abnormal TSH test

The analyses will be conducted using the 30-day safety window.

A by-subject listing of these specific abnormalities will be provided.

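### The 30-day cutoff for the abnormal liver and thyroid tables falls in the middle of the FU1 visit window, so some protocol-compliant FU1 values never reach the arm-level counts; a supplementary 100-day repeat would capture most of them

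*SAP*

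**What the plan says.** **Window.** SAP 6.1 offers two windows for laboratory data after treatment ends: "evaluations should be within a safety window of 30 days (or 100 days depending on the analysis) after the last dose of study treatment". SAP 7.6.10.4 selects one for the abnormal hepatic and thyroid function tables: "The analyses will be conducted using the 30-day safety window". It also restricts the source data, because the "laboratory abnormalities from on-treatment evaluations will be summarized by treatment group". No 100-day repeat is planned.

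**Pairs.** The hepatic table counts participants with raised transaminases and raised bilirubin close together in time. One row reads "Concurrent (within 30 days) ALT or AST > 3 x ULN and total bilirubin > 2 x ULN". The others use a 1-day interval or a bilirubin threshold of 1.5 x ULN.

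**Visits.** Protocol Table 2-5, footnote a, sets the first follow-up visit: "Follow-up visit #1 (FU1) should occur 30 days from the last dose (+/- 7) days or can be performed on the date of discontinuation", the latter "if that date is greater than 42 days from last dose". The laboratory row of that table reads "FU1 -yes FU2 - if toxicities are present". The FU1 panel includes AST, ALT, total bilirubin, ALP and TSH with reflexive free T3 and T4.

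**The concern.** The cutoff for the tables is the target day of the one post-treatment panel that everyone should have. A site can perform FU1 on day 33, fully within the protocol, and its liver and thyroid results will not enter the tables designed to display them. A visit on day 29 would count. Inclusion then depends on which side of day 30 a permitted visit happens to fall.

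What is at stake is the completeness of two descriptive safety tables. A first abnormal value, or a value that completes an ALT/AST and bilirubin pair, could be missing from the arm-level count. PFS, OS and ORR are not touched.

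**Working it through.** The plan gives no figure to reproduce here; the check is a count of days after last dose.

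**Inputs.** Cutoffs: 30 and 100 days (SAP 6.1). FU1: day 30 ± 7, or at discontinuation if later than day 42. FU2: day 100 ± 7 (Protocol Table 2-5). Pairing interval: up to 30 days (SAP 7.6.10.4).

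**1. FU1 against the cutoffs.** The scheduled window is days 23 to 37: 37 − 23 + 1 = 15 days.

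| Cutoff | FU1 days inside | FU1 days outside |
|---|---|---|
| 30 days | 23–30: 8 of 15 | 31–37: 7 of 15 |
| 100 days | 23–37: 15 of 15 | 0 of 15 |

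An FU1 done at discontinuation after day 42 is always outside 30 days. It is inside 100 days only if done by day 100.

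**2. FU2 against the cutoffs.** The window is days 93 to 107, 15 days. None is inside 30 days. Days 93 to 100, 8 of 15, are inside 100 days; days 101 to 107 are not.

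**3. Pairs within one panel.** ALT, AST and bilirubin are in the same FU1 chemistry panel. If both are raised at an FU1 on day 35, the pair is complete on one date and is still excluded, because 35 > 30. No unscheduled draw is needed for this loss.

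**4. Pairs across two dates.** If the first value is on or before the day of last dose (day 0 or earlier), a partner within 30 days falls on day 30 or earlier, inside the cutoff. A pair across dates is therefore lost only when both draws are after last dose. Example: ALT > 3 x ULN on day 14 and bilirubin > 2 x ULN at FU1 on day 35 are 35 − 14 = 21 days apart. They satisfy the 30-day pairing rule, but the second value is excluded. Table 2-5 schedules no panel between last dose and FU1, so the day-14 value would come from additional monitoring, such as the re-evaluation during dose delays (Protocol 7.4.1) or the follow-up of laboratory toxicities (Protocol Section 9).

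**5. Comparison with other SAP tables.** Hematology, chemistry and electrolytes (7.6.10.1 to 7.6.10.3), select AEs (7.6.6) and SAEs (7.6.2: "All analyses will be conducted using the 30-day safety window") use 30 days. The drug-related AE table by grouped grade is run at 30 days and repeated at 100 (7.6.5). IMAE and OEOSI tables use 100 days (7.6.7, 7.6.8).

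**The case against.** The strongest reply is that this is a reporting choice, properly made. SAP 6.1 leaves the window to each analysis, 7.6.10.4 states it, and every visible laboratory section uses the same 30 days. The 100-day tables count reported events, not laboratory thresholds. That stands: a reader might infer that the SAP contradicts itself or the protocol, and it does not.

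Existing cover is also real, though partial:

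- **Thyroid.** Endocrine IMAEs are tabulated by arm to 100 days, regardless of causality and without requiring immune-modulating medication (SAP 7.1.1.3, 7.6.7). The thyroid gap is mainly abnormal values not recorded as qualifying AEs.
- **Liver.** Potential drug-induced liver injury must be reported as an SAE (Protocol 9.2.7), and SAEs are collected to 100 days (9.2.1). One with onset after day 30 would be in the SAE listing but not in the 30-day SAE table; if judged drug-related, it would be in the 100-day drug-related AE table. That definition requires bilirubin above 2 x ULN and excludes cholestasis and other apparent causes, so it is narrower than the SAP's rows. Hepatitis IMAEs require immune-modulating medication.
- **Single values.** Clinically significant results are recorded as AEs (Protocol 9.2.6), and by-subject listings are planned. The listing in 7.6.10.4 may carry the same 30-day limit.

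None of these gives an arm-level count by laboratory threshold.

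A last objection is that a 100-day count is harder to interpret. Later tests are taken selectively, and some values may reflect subsequent therapy. This also stands, and it is why the repeat should be supplementary.

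**Conclusion.** The point holds as a low-priority improvement. The 30-day limit excludes FU1 values on 7 of the 15 scheduled days and every FU1 after day 42, together with pairs completed by those values.

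An excluded value changes a table only if the participant had not already met that criterion within the window, or if the value completes a pair. The conclusion rests on reading on-treatment in 7.6.10.4 through the SAP 6.1 definition, and on the visible text, since parts of the SAP are redacted.

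Four stronger readings are not supported:

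- **That 7 of 15 (47%) is the share of FU1 panels lost.** It is a share of permitted days. The documents do not give the distribution of visits within the window, and the number of participants affected cannot be estimated.
- **That a calculable share of late pairs is lost.** Counting the calendar days of the 30-day pairing interval that lie beyond the cutoff treats every day as if a sample were due. Apart from the FU1 panel itself, those days depend on unscheduled draws.
- **That the cutoff biases the comparison between arms.** Both arms have the same FU1 rule and cutoff, and nothing in the documents shows a differential loss.
- **That a 100-day window recovers everything.** It misses an FU1 after day 100 and FU2 values on days 101 to 107.

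**What to change.** Keep all 30-day tables and add to SAP 7.6.10.4:

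> The abnormal hepatic and thyroid function tables, including the concurrent ALT/AST and total bilirubin counts, will be repeated as supplementary tables using the 100-day safety window; values drawn after the start of subsequent anti-cancer therapy will be identified in the by-subject listing.

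The identification belongs in the listing because the tables count participants, so a single value cannot be marked in them. The listing should itself run to 100 days.

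The cost is two repeated tables and one added item in a listing, with no new data collection. The 100-day window is already defined in SAP 6.1, and the paired 30-day and 100-day format is already used in SAP 7.6.5. The 100-day counts should be labelled supportive because of the selective late sampling. They should not be expected to match the IMAE counts, which are defined differently.

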6.2 Treatment Regimens

The treatment group “**as randomized**” will be retrieved from the IRT system:

- Arm A: Experimental arm: nivolumab + cabozantinib
- Arm B: Experimental arm: nivolumab + ipilimumab + cabozantinib
- Arm C: Control arm: sunitinib

The treatment group “**as treated**” will be the same as the arm as randomized by IRT. However, if a subject received the incorrect drug for **the entire period** of treatment, the subject’s treatment group will be defined as the incorrect drug the subject actually received.

Unless otherwise specified, the safety analysis will be based on the treatment group “as treated”.

Unless otherwise specified, the efficacy analysis will be based on the treatment group “as randomized”.

6.3 Populations for Analyses

All analyses will be performed using the treatment arm as randomized (intent to treat), with the exception of dosing and safety, for which the treatment arm as received will be used. For purposes of analysis, the following populations are defined in [Table 6.3-1](#), and all populations for analyses given in this table refer to those subjects in Arm A and Arm C. Those subjects who randomized to Arm B prior to Revised Protocol 01 will be considered as part of the population of interest for descriptive summary of efficacy and safety analyses.

Table 6.3-1: Populations for Analyses

Population	Description
All Enrolled Subjects	All subjects who sign informed consent and were registered into the IRT.
All Randomized Subjects	All subjects who were randomized will be used for analyses of demography, protocol deviations, baseline characteristics, primary efficacy analysis, secondary efficacy analyses, and outcome research analysis which will be performed for this population.
All Treated Subjects	All subjects who received at least one dose of any study medication. This is the primary population for exposure and safety analyses.
Intermediate/Poor Risk Subjects	All subjects who were randomized with baseline IMDC prognostic score ≥ 1 at the time of randomization (per IRT). This population will be used for subset analyses of demography, protocol deviations, baseline characteristics, primary efficacy analysis, and secondary efficacy analyses on intermediate/poor risk subjects.
All Intermediate/Poor Risk Treated Subjects	All intermediate/poor risk subjects who received any dose of study therapy. This population will be used for subset analyses of exposure and safety analyses on intermediate/poor risk subjects.
[REDACTED]	[REDACTED]
[REDACTED]	[REDACTED]
[REDACTED]	[REDACTED]

7 STATISTICAL ANALYSES

7.1 General Methods

Unless otherwise noted, discrete variables will be tabulated by the frequency and proportion of subjects falling into each category, grouped by treatment. Percentages given in these tables will be rounded to the first decimal and, therefore, may not always sum to 100%. Percentages less than 0.1 will be indicated as '< 0.1'. Continuous variables will be summarized by treatment group using the mean, standard deviation, median, minimum, and maximum values.

Time-to-event variables (e.g. time-to resolution) will be analyzed using the Kaplan-Meier technique. When specified, the median will be reported along with 95% CI using Brookmeyer and Crowley method⁵ (using log-log transformation for constructing the confidence intervals⁶).

Unless otherwise specified, the stratified log-rank test will be performed to test the comparison between time to event distributions. Unless otherwise specified, the stratified hazard ratio between 2 groups along with CI will be obtained by fitting a stratified Cox model with the group variable as a unique covariate.

Confidence intervals for binomial proportions will be derived using the Clopper-Pearson method.⁷ The unweighted difference in ORRs between the two treatment arms and corresponding asymptotic 95% CI will be estimated using a Newcombe method.⁸

P-values from sensitivity analyses for efficacy endpoints are for descriptive purpose only and there will be no multiplicity adjustment for these analyses.

The conventions to be used for imputing missing and partial dates for analyses requiring dates are described in [Section 8](#).

Note that, the outputs will present Arm A, Arm B, and Arm C in the following way:

- All analysis specified in [Section 7.3](#) and [7.4](#) will present A, B, and C together.
- For purposes of efficacy analyses, all randomized subjects in Arm A and Arm C will be tabulated and presented in the same table. A few separate efficacy summary tables will be generated for those subjects randomized to Arm B, which will be specified in the corresponding sections.
- For purposes of safety analyses, all treated subjects in Arm A and Arm C will be tabulated and presented in the same table. A few separate safety summary tables will be generated for those subjects treated in Arm B, which will be specified in the corresponding sections.
- Summaries of outcome research and biomarker data will be tabulated on the Arm A and C subjects only.

7.1.1 Adverse Events, Serious Adverse Events, Multiple events, Select Adverse Events, Other Events of Special Interest and Immune-Mediated Adverse Events

Drug-related AEs are those events with relationship to study drug “Related”, as recorded on the CRF. If the relationship to study drug is missing, the AE will be considered as drug-related.

Serious adverse events consist of AEs deemed serious by the Investigator and flagged accordingly in the CRF and clinical database.

Adverse events leading to study drug discontinuation are AEs with action taken regarding study drug(s) = “Drug was discontinued”.

Adverse events leading to dose delay are AEs with action taken regarding study drug(s) = “Drug was delayed”.

Adverse event that led to dose delay of the oral drug (similarly defined as dose omission or dose interruption) will be coded with action “Drug was interrupted”.

Adverse events leading to dose reduction are AEs with action taken regarding study drug(s) = “Dose was reduced”.

Adverse events will be coded using the Medical Dictionary for Regulatory Activities (MedDRA), and the most recent version of the dictionary at the time of the database lock will be used. Adverse events results will be graded for severity using NCI Common Terminology Criteria for Adverse

Events (CTCAE) and the most recent version of the criteria at the time of the database lock will be used.

In the AE summary tables, unless otherwise specified, subjects will be counted only once at the Preferred Term (PT), only once at the System Organ Class (SOC), and only once at subject level for the counting of total number of subjects with an AE. The AE tables will be sorted by the SOCs and then PTs. SOC will be ordered by descending frequency overall and then alphabetically. PTs will be ordered within SOC by descending frequency overall and then alphabetically. The sorting will be done based on the 'Any Grade' column of the experimental arm when arms are presented side-by-side.

Unless otherwise specified, the AE summary tables will be restricted to on-treatment events regardless of the causality.

Analyses that take into account the multiple occurrences of a given adverse event will be conducted (see [Section 7.6.9](#)). To prepare these analyses, the CRF data will be processed according to standard BMS algorithms⁹ in order to collapse adverse event records into unique records based on the preferred term. These data will be presented as the rate per 100 person-years of exposure. These analyses will take into account all on-treatment events (allowing more than 1 event per subject) and the total exposure time. The person-year exposure will be computed as the sum over the subjects' exposure expressed in years where the exposure time is defined as

- $(\text{Date of last dose of study treatment} - \text{date of first dose of study treatment} + 31 \text{ days (or 101 days, depending on the analysis)}) / 365.25$, for subject who are off study treatment and were followed for at least 30 days (or 100 days, depending on the analysis) after last dose of study treatment.
- $(\text{Last known alive date} - \text{date of first dose of study treatment} + 1) / 365.25$, for subjects who are still on-treatment or who are off study treatment and were followed less than 30 days (or 100 days depending on the analysis) after last dose of study treatment.

